### **5.2.4. Safety Analysis Set (SAF)**

The safety analysis set will include all subjects who receive any dose of study medication. All safety data will be analyzed using the SAF. Subjects will be analyzed according to the treatment actually received.

## **5.3. General Data Handling Rules and Presentation Specifications**

The following general guidelines will apply to all statistical analyses and data presentations:

### **5.3.1. Analysis Period**

#### **5.3.1.1. On-Study Period**

Unless otherwise specified, the efficacy analysis will be based on the on-study period, which is defined as from randomization to the day of last efficacy assessment for the main study period prior to first study drug infusion in the OLE period for subjects who enrolled in the OLE period; or from randomization to the last day of any efficacy assessment for subjects who didn't enroll in the OLE period.

For the safety analysis, all safety assessments beyond 60 days of last dose will be excluded from summary tables or figures.

### 5.3.1.2. On-Treatment Period

The on-treatment analysis includes only the assessments that are observed during On-Study Period as defined above ([Section 5.3.1.1](#)), or within 4 weeks after last study drug infusion in the main study period. On-treatment analysis as one of the sensitivity analyses will only be conducted for the primary efficacy endpoint.

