4.3. Subject Withdrawal Criteria

Subjects may withdraw from the study at any time, for any reason. If a subject or investigator determines subject should discontinue from treatment, the subject has the option to remain on study. If the subject remains on study, they should continue to perform on-study assessments until the end of study visit or subject terminates for one of the below reasons.

Mandatory reasons for withdrawing the subject from the study include the following:

- Any safety concern in the Investigator's opinion, that precludes further study participation
 - Pamrevlumab will be permanently discontinued in case of serious or life-threatening allergic reactions
- Major protocol deviation to inclusion/exclusion that substantially affects subject safety
- Withdrawal of Consent (reason of withdrawal should be obtained)

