### 5.3.5. Handling Dropouts and Missing Data

All assessments collected will be considered for analyses regardless of whether such data are collected during treatment or after a subject discontinued treatment. All analyses assume the

missing data are missing at random (MAR), unless stated otherwise. Detailed missing data handling are described in the analysis of specific endpoints.

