### **6.6.1.1. Primary Analysis with the Random Coefficient Model (RCM)**

#### **6.6.1.1.1. Estimand Strategy**

The primary estimand is intended to provide a population level estimate of the treatment effect of the pamrevlumab on a continuous endpoint, regardless of participant compliance with the IP dosing. Treatment policy strategy will be implemented, which means all observed measurements after randomization will be used in the primary analysis.

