#### 6.6.1.1.4. Analysis Variable

Change from baseline in the total score of all PUL assessments in the randomization treatment period, including scheduled, unscheduled, and available assessments after treatment discontinuation, up to the targeted week 52 during the On-Study period ([Section 5.3.1.1](#)), will be included in the analysis.

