##### 6.6.1.2.6.1. Estimand Strategy

Same as [Section 6.6.1.1.1](#)

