##### 6.6.1.2.6.4. Analysis Variable

Only on-treatment PUL assessments will be included in the analysis

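### As written, the on-treatment analysis removes no off-treatment PUL score, and the jump-to-control sample code uses the placebo model only at Week 52

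*SAP*

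**What the plan says.** **On-treatment analysis.** SAP 5.3.1.2 keeps assessments in the On-Study Period "or within 4 weeks after last study drug infusion in the main study period". SAP 5.3.1.1 describes the On-Study Period, for subjects who enter the extension, as "defined as from randomization to the day of last efficacy assessment for the main study period" before the first extension infusion. For other subjects it runs to the last efficacy assessment of any kind. Neither version ends when dosing stops.

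PUL scores after dosing stops are expected. Protocol 4.3 lets a subject stop treatment and stay: "If the subject remains on study, they should continue to perform on-study assessments until the end of study visit". SAP 5.3.5 uses data "regardless of whether such data are collected during treatment or after a subject discontinued treatment", and the primary analysis variable (SAP 6.6.1.1.4) includes "available assessments after treatment discontinuation, up to the targeted week 52".

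For the on-treatment analysis, SAP 6.6.1.2.6.4 says: "Only on-treatment PUL assessments will be included in the analysis". Its estimand strategy (6.6.1.2.6.1) is a cross-reference to the treatment-policy strategy of 6.6.1.1.1, under which "all observed measurements after randomization will be used in the primary analysis".

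**Jump-to-control.** SAP 6.6.1.2.4.3 gives pamrevlumab subjects the placebo pattern once they withdraw, and gives placebo dropouts the pattern of the placebo subjects who remain. Step 1 of 6.6.1.2.4.5 says imputation follows that rule. The sample code there lists baseline and Weeks 16, 28, 40 and 52 in its `VAR` statement, without treatment. Its single `MNAR MODEL` statement names Week 52 only. The delta-adjusting code in 6.6.1.2.5.5 has an `MNAR` statement for each of the four visits.

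**The concern.** A sensitivity analysis is useful only if it changes the assumption it claims to change. If the first definition is programmed literally, a table labelled on-treatment would agree with the primary result because it uses the same scores, and a reader would take that as support. If the second is programmed from the sample code, the table would not follow the missing-not-at-random rule stated for it, and the direction of the error would depend on which arm loses more subjects.

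The copied treatment-policy label is a further problem. Once off-treatment scores are dropped, the model no longer estimates a treatment-policy effect.

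**Working it through.** **Inputs.** Planned difference 2.0 and SD 2.9 (SAP 3.3); PUL visits at Weeks 16, 28, 40 and 52 (SAP Appendix 2, Table 9); infusions every 2 weeks; early termination visit at 28 +/- 3 days (Protocol 4.4). The documents give no dropout rates, so those below are assumed. The planning figures reproduce: a two-sample t-test has 90.5% power with 46 per arm (92 in total) and 87.0% with 41 per arm (82, SAP Section 7).

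**1. Set logic.** Let S be the On-Study assessments and W those within 4 weeks of the last infusion. The definition is S or W, which contains all of S. No other rule restricts PUL: the 60-day rule in 5.3.1.1 is for safety data, and the 60-day note under Table 9 is worded for laboratory summaries.

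**2. What a real cut would remove.** Take a subject who stops dosing and stays on study. There are 26 possible last-infusion weeks before Week 52 (0, 2, ..., 50) and four PUL visits, so 26 x 4 = 104 slots.

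| Last infusion week | Weeks in range | Visits more than 28 days later | Slots removed |
|---|---|---|---|
| 0-10 | 6 | 4 | 24 |
| 12-22 | 6 | 3 | 18 |
| 24-34 | 6 | 2 | 12 |
| 36-46 | 6 | 1 | 6 |
| 48-50 | 2 | 0 | 0 |

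The total is 60 of 104 with *and*, and 0 of 104 with *or*. On nominal dates the count is the same at 31 days.

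**3. The 4-week limit.** Early termination falls on days 25 to 31. A strict 28-day cut would drop a PUL done on days 29, 30 or 31, which is 3 of the 7 allowed days.

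**4. Why the strategy label matters.** Assume 20% of each arm stop evenly over Weeks 0-46 and stay on study, and that benefit stops accruing when dosing stops. The mean stopping time is Week 23, so the treatment-policy value is 0.8 x 2.0 + 0.2 x 2.0 x (23/52) = 1.78. A random-coefficient fit (300,000 simulated subjects per arm, measurement SD 0.5 to 1.5) gives 1.79 to 1.80 on all scores and 1.99 to 2.00 on scores cut at 31 days. The restricted analysis therefore targets the effect under continued treatment.

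**5. Jump-to-control, one dropout.** Take a linear effect reaching 2.0, arms of equal size, between-visit correlation 0.5 and no post-baseline score. Pooled imputation places the subject above the placebo mean by half the effect:

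- Week 16: 0.5 x 2.0 x 16/52 = 0.308
- Week 28: 0.5 x 2.0 x 28/52 = 0.538
- Week 40: 0.5 x 2.0 x 40/52 = 0.769

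The placebo regression for Week 52 weights each by 0.5/(1 + 2 x 0.5) = 0.25. The excess is 0.25 x 1.615 = 0.40, against 0 with the placebo model at every visit.

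Across compound-symmetry and random-slope covariances (parameter 0.5 to 0.9), the excess for a pamrevlumab dropout is 0.40-0.90 with nothing observed, 0.25-0.53 with Week 16 observed, 0.12-0.24 with Weeks 16 and 28 observed, and 0 if only Week 52 is missing.

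**6. Jump-to-control, arm difference.** Placebo dropouts are also imputed from the pooled model, so the shifts largely cancel when dropout is equal. For 20% against 5% with nothing observed, the shift is roughly (0.20 - 0.05) x 0.40 = 0.06 to (0.20 - 0.05) x 0.90 = 0.14. Expectations were then computed over 81 settings: measurement SD 0.5/1.0/1.5, baseline SD 4/6/8, baseline-slope correlation -0.3/0/0.3, placebo change -1/-2/-3. Equal dropout gave 0.003 or less.

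| Dropout, pamrevlumab vs placebo | Timing | Code as written minus placebo model at all visits |
|---|---|---|
| 15% vs 10%, or the reverse | even | about 0.02 either way |
| 20% vs 5% | even | +0.04 to +0.06 |
| 5% vs 20% | even | -0.05 to -0.06 |
| 20% vs 5% | all before Week 16 | +0.08 to +0.13 |
| 5% vs 20% | all before Week 16 | -0.10 to -0.15 |

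**The case against.** The intent of the on-treatment section is plain. Its heading, the word *only* in 5.3.1.2 and the wording of 6.6.1.2.6.4 all point to a restriction, so a careful programmer would probably apply one. The table specifications are a separate document, not seen here. That makes the harm conditional, but 5.3.1.2 is the definition the section relies on, and it says the opposite.

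The missing-data handling is partly in place. 6.6.1.2.6.3 points to 6.6.1.1.3, which treats data missing after discontinuation as missing at random. What remains is the wrong strategy label and the lack of a statement that scores after the cut are set to missing. The early termination clash arises only once *or* becomes *and*, so it is a drafting point for the correction and not a separate error.

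The jump-to-control code is headed as sample code, and other samples in the SAP contain placeholders. The text states the rule correctly. Even so, the code is the only operational specification of that analysis, and it contradicts the text. Leaving treatment out of `VAR` is not a fault in itself. The gap is the three visits absent from the `MNAR` statement.

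The shifts are small. With 41 per arm the standard error of a simple difference is 2.9 x sqrt(2/41) = 0.64, so 0.06 is about 0.09 of a standard error and 0.15 about 0.23. The 104 slots weight every stopping week equally, so 60 is not an expected data loss, and 1.78 against 2.00 contrasts two estimands without showing bias in the primary result. All of this stands and limits the importance of the point. It does not remove the contradictions.

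**Conclusion.** Both points hold. Read literally, the on-treatment data set is at least as large as the primary one and removes no off-treatment score. This follows from the wording alone and needs no assumption. The jump-to-control code departs from its stated rule for any subject missing Week 40 or earlier. The size of that departure rests on assumed dropout, timing and covariance: negligible when dropout is balanced, and up to 0.15 of the planned 2.0 points in the most unbalanced, earliest case examined.

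Both analyses lie outside the testing sequence in SAP Table 1, so the primary test, alpha and sample size are untouched. Other analyses cover part of the gap: the per-protocol set drops whole subjects who stopped early, the loss-of-function analysis censors at discontinuation, and the delta-adjusting analysis covers all four visits. None of them is the on-treatment analysis the SAP promises. The correction should be made, because each table would otherwise carry a label that its method does not support.

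**What to change.** 1. **SAP 5.3.1.2:** replace *or* with *and*, so that the set is On-Study assessments no later than 4 weeks after the last main-study infusion, with the Week 52 limit of 6.6.1.1.4. Reconcile the 4 weeks with the early termination window, for example by setting the analysis limit at 31 days.
2. **SAP 6.6.1.2.6.1 and 6.6.1.2.6.3:** replace the treatment-policy cross-references with a hypothetical strategy for treatment discontinuation. State that scores after the cut are set to missing and handled under missing at random, so that the model estimates the Week 52 difference as if treatment had continued. Keep the death rule of 6.6.1.1.3.
3. **SAP 6.6.1.2.4.5:** first make the data monotone as in Step 1a of 6.6.1.2.3.5. Then run `PROC MI` by `_IMPUTATION_` with `NIMPUTE=1` and `MNAR MODEL (WEEK16 WEEK28 WEEK40 WEEK52 / MODELOBS=(TRTP='Placebo'))`. Describe the result as placebo-based imputation conditional on the subject's earlier scores, because sequential regression keeps part of any benefit seen before withdrawal. The delta-adjusting code also uses `MONOTONE REG`, so the same monotone step can serve both.

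The cost is a few SAP lines and minor programming, with no new data. The on-treatment estimate becomes slightly less precise because scores are removed.

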### 5.3.2. Baseline and Change from Baseline Definitions

Baseline is defined as the last available value obtained prior to the first dose of study drug (or randomization date if no infusion received) if not specified otherwise ([Section 5.5](#)). The acceptable value on Day 1 will be used to define the baseline values. Unscheduled visits will be considered for baseline.

Change from baseline will be calculated by subtracting the baseline value from the post-dose assessment for each subject.

### 5.3.3. Study Day Calculation

The day when a subject receives the first dose of study drug after randomization will be considered as Day 1 for all analysis.

Study day of an assessment/procedure is calculated as follows.

- For events on or after first dose:  
$$\text{Study day} = \text{Event date} - \text{Day 1 date} + 1.$$
- For events earlier than first dose:  
$$\text{Study day} = \text{Event date} - \text{Day 1 date}.$$

Note: Day 1 date will be the first dose date if the subject receives study treatment. Otherwise, it will be the randomization date if the subject does not receive the study treatment after randomization.

### 5.3.4. General Instructions on TFLs

For continuous variables that are recorded as “<X” or “>X”, the value of “X” will be used in the calculation of summary statistics.

All percentages will be rounded to one decimal place. The percentage will be suppressed when the count is zero. All durations of time will have 1 decimal place.

All tables and listings will have a header showing “FibroGen, Inc.”, protocol number (study nickname), date of data cutoff, and Page x of y. A footer will show the program file path/name, date of data extraction, run date and run time.

More details are available in [Appendix 5](#).

### 5.3.5. Handling Dropouts and Missing Data

All assessments collected will be considered for analyses regardless of whether such data are collected during treatment or after a subject discontinued treatment. All analyses assume the

missing data are missing at random (MAR), unless stated otherwise. Detailed missing data handling are described in the analysis of specific endpoints.

#### **5.4. Interim Analysis and Data Monitoring Committee**

In addition to routine safety monitoring, an independent DMC is established to review safety data on an ongoing basis. A DMC charter will establish the procedures, meeting frequency, and scope of responsibilities of the committee.

This study has no planned or pre-specified interim analysis for either efficacy or futility.

#### **5.5. Analysis Visit Windows**

In accordance with FDA/EMA Guidance: During the COVID-19 pandemic, the visit modality (e.g.: in-person versus remotely) and scheduling may be adjusted and conducted at the discretion of the Investigator, in accordance with the site's rules and recommendations, and using all necessary precautions. If a visit must be done remotely, it can be conducted with any technology available to the site and study subjects, such as via tele-health visits, phone calls, etc.

Analysis visits, instead of the nominal visits from case report form (CRF), derived from visit dates and visit time windows will be used in the by-visit analyses. Unscheduled visits within a visit window (defined in [Appendix 2](#)) will be grouped into the closest scheduled visits based on the visit date. For subjects who have more than one measurement at a certain analysis visit, the measurement closest to the target date or the later assessment if there is a tie will be used, with the following exceptions:

- Liver function tests, such as Alanine Aminotransferase (ALT), Aspartate Aminotransferase (AST), Gamma-Glutamyl transferase (GGT), Alkaline Phosphatase (ALP), and total bilirubin, in which the maximum value will be used.
- Vital signs: the values on the infusion days will be used if applicable.
- Spirometry data: the Best Test Read (BTR) values will be used for analysis.

Efficacy parameters will be summarized by analysis visit defined by the following assessment windows ([Appendix 2](#)). The date of the first dose will be considered as the date of Day 1 for all analyses. Subjects will receive study drug every 2 weeks. The visit window for these visits is  $\pm 3$  days. Duchenne Video Assessment is to be performed in the subject's home up to 14 days prior to the scheduled study visit.

## **6. STATISTICAL ANALYSES**

### **6.1. Subject Enrollment and Disposition**

#### **6.1.1. Eligibility**

Eligibility will be summarized for all screened subjects. The data will be summarized with respect to:

- number of subjects screened

- number (%) of subjects screen-failed
- number (%) of subjects for each failed inclusion/exclusion criterion

Subject level inclusion criteria not met/exclusion criteria met listings will be provided.

### **6.1.2. Subject Accountability and Disposition**

The number (%) of subjects randomized (ITT), dosed (SAF), mITT, Per-Protocol Set (PPS), completed the main study, entered the OLE period, and discontinued prematurely from treatment and study in the main study will be presented for each treatment group and for all subjects pooled.

Reasons for premature discontinuation of treatment in the main study will be summarized by treatment group for the ITT population. A listing for the subjects who discontinue treatment prematurely in the main study will be presented.

## **6.2. Important Protocol Deviations**

Important protocol deviations of interest may include, but are not limited to, the following:

- Entry Deviation: Subjects who entered the study, but did not meet inclusion/exclusion criteria;
- Withdrawal Deviation: Subject met withdrawal criteria during the study but was not withdrawn;
- Dosing Deviation: Subject received the wrong treatment or incorrect dose; including incorrect timing of a dose; or subjects who missed more than 10% doses of prescribed study medication during the overall treatment period;
- Prohibited Medication Deviation: Subject received disallowed concomitant medications or non-drug therapy.

All above protocol deviations will go through the medical review process.

A subset of pre-specified important protocol deviations will be defined as major protocol deviations and subjects with major protocol deviations will be excluded from PPS analysis. The number and percentage of subjects with important protocol deviations will be categorized and tabulated as appropriate for the ITT population. COVID-19 related important protocol deviations will be summarized separately. All protocol deviations will be finalized prior to database lock and unblinding.

## **6.3. Demographics and Baseline Characteristics**

Demographics and baseline characteristics will be summarized descriptively for subjects in mITT, ITT and SAF. Each parameter will be presented in data listings.

Baseline values for efficacy assessments will be presented in baseline tables as appropriate.

### **6.3.1. Demographics and Baseline Characteristics**

Demographic parameters and other important baseline and disease characteristics will be summarized by treatment group. These include but may not be limited to age, age group ( $\leq 16$

years, >16 years), ethnicity, race, weight, body-mass index (BMI), side of dominant hand, and body surface area (BSA), PUL 2.0 total score and subscores.

Computation formula:

$$BSA = [\text{Weight}^{0.425} (\text{kg}) * \text{Height}^{0.725} (\text{cm})] \times 0.007184$$

$$\text{Age} = \text{Year of informed consent date} - \text{Year of birth}$$

Height (cm) = 4.605 \* Ulna length (cm) + 1.308 \* Age at PFT assessment + 28.003, where age < 18 years old during PFT visits; For subjects that enter the study at age 18 or turn 18 during the study, the last recorded ulna length/height will be used for the remainder of the study.

Descriptive statistics (n, mean, standard deviation, median, interquartile (Q1, Q3), range (=minimum, maximum)) will be presented for continuous variables. Frequency distributions (number and percentage of subjects) will be presented for categorical variables.

### 6.3.2. Baseline DMD Disease Characteristics

Baseline DMD disease characteristics include, but not limited to,:

1. Age in years when DMD was diagnosed = Year of date of diagnosis - Year of birth
2. Age when subject became non-ambulant = Year of date of when subject became non-ambulant - Year of birth
3. Years since subject became non-ambulant = Current age – Age when subject became non-ambulant
4. Age when subject began ventilation support = Year of date of subject began ventilation support - Year of birth
5. Ventilation support: yes or no. If yes, years since subject began ventilation support = Current age – Age when subject began ventilation support.
6. Corticosteroids use: yes or no. If yes, age when subject began corticosteroids (= Year of date of subject began corticosteroids - Year of birth), and years since subject began corticosteroids = Current age – Age when subject began corticosteroids.
7. Spine surgery: yes or no. If yes, age when spine surgery (= Year of date of subject began spine surgery - Year of birth) was done, and years since the most recent spine surgery = Year of Day 1 Visit Date - Year of spine surgery,
8. Genetic characteristics (check all that apply)
  - Exonic deletion
  - Duplication
  - Point mutation
  - None of above
  - Unknown

Additionally, the following baseline disease characteristics, but are not limited to, will be summarized.

9. Bone parameters
  - Bone fractures ([Section 6.8.8](#))
  - Scoliosis
  - Osteoporosis
  - Spine surgery
10. Cardiac parameters
  - Cardiomyopathy
  - LVEF (%)
11. Respiratory parameters
  - Ventilation support
  - Years since ventilation support
  - Sleep apnea
  - ppFVC
12. Metabolic parameters
  - Insulin resistance
  - Obesity
  - Vit D deficiency
  - Delayed puberty
13. Corticosteroids (CS) use
  - Age at CS initiation
  - Prednisone/Prednisolone
  - Deflazacort
  - Regimen
    - Daily
    - Other

### 6.3.3. Medical History

Medical History of interest including allergies and surgeries, coded in system organ class (SOC) and preferred term (PT) using MedDRA (version 26.0 or higher), will be summarized for the ITT Analysis Set. Subject medical history listings will be provided.

